Subjects who are positive for *C. difficile* toxin should be screen-failed; these subjects may be re-screened after completing the appropriate treatment. For subjects who are borderline for *C. difficile* toxin, the investigator may send another sample for a test. If the result is negative, the investigator may consider the test to be negative based on his/her judgment. If the result is positive or borderline, the test is considered positive and subject should be screen failed. For those subjects with two borderline results, the PI can decide if *C. difficile* treatment is needed based on his/her clinical judgment; these subjects may be re-screened with or without *C. difficile* treatment.

Outcomes and Questionnaires

The following outcomes and questionnaires will be completed at the time points indicated in [Appendix C](#) and [Appendix D](#). However, please ensure questionnaires are always completed prior to obtaining blood samples. Refer to [Appendix E](#) for descriptions of Patient Reported Outcomes.

- IBDQ – Inflammatory Bowel Disease Questionnaire
- SF-36 – Short Form 36
- EQ-5D-5L – European Quality of Life 5 Dimensions 5 Levels
- FACIT-F – Functional Assessment of Chronic Illness Therapy-Fatigue

- WPAI – Work Productivity and Activity Impairment Questionnaire Ulcerative Colitis
- PGIC – Patient Global Impression of Change
- PGIS – Patient Global Impression of Severity (only in select sites)
- UC-SQ – Ulcerative Colitis Symptoms Questionnaire
- HCRU – Supplemental Hospitalization and Surgery forms

COVID-19 Pandemic-Related Acceptable Protocol Modifications

Due to the COVID-19 pandemic, subject visits may be conducted via phone or video conference, except baseline. All PROs, except EQ-5D-5L scale, are eligible for completion by interview. If there are time constraints to the phone visit, at a minimum, the following PROs must be completed:

- Inflammatory Bowel Disease Questionnaire (IBDQ)
- Functional Assessment of Chronic Illness Therapy-Fatigue (FACIT-F)
- Patient Global Impression of Change (PGIC)
- Patient Global Impression of Severity (PGIS)

Prior to conducting any phone visits to obtain PRO data the site staff person should be delegated this task on the Delegation of Authority log. Sites will read the PRO questions and response options to the subject and record the subject's responses. The subject's ability to view the PRO to understand the questions and response options should be preserved. Sites must share a local language version of the questionnaire by videoconference or send the questionnaires (email or hard copy) to the subjects to allow them to read/understand the questions and responses when the subject is providing responses over the phone. The date and start and stop time of PRO data collection should be recorded along with who collected the information, their role and which questionnaires were completed.

Subject Diary

Subjects will be dispensed an electronic diary (eDiary) at Screening and the site staff will enter the NORMAL baseline number of stools in a 24-hour period when the subject's UC is **not** active to allow for scores to be calculated.

Subjects will be trained on how to complete the diary by site staff during the Screening Visit. All subjects should complete their subject diary on a daily basis throughout the entire study. The diary will be reviewed by site personnel with the subject at each visit and collected at the Final/PD Visit. If subjects require re-training during the study, the site staff will accommodate this requirement.

In case of missing diary information, or when discrepancies are discovered, site personnel should discuss with the subject and document changes in site records, if applicable. Completion will be reinforced during study visits as necessary as the diary data required to be entered by the subject(s) cannot be changed or altered in any way.

Study Drug Dispensing/Administration

Study drug will be dispensed to subjects at the time points indicated in [Appendix C](#) and [Appendix D](#).

Study drug will be taken orally once daily beginning at the Baseline Visit and should be taken at approximately the same time each day. At scheduled visits, study drug should be administered after all assessments and examinations scheduled for that day have been completed if the visit occurs at the time the subject is taking study drug each day. If study drug is being taken earlier than when the visit is set to occur, the time of the last two doses will be documented in the eCRF and pharmacokinetic (PK) samples drawn at the visit.

Refer to Section [5.5](#) for additional information.

COVID-19 Pandemic-Related Acceptable Protocol Modifications

Drug may be only dispensed to subjects if specific Laboratory result criteria are met; please see these outlined below and refer to the Clinical Laboratory Tests section above for more information.

If laboratory samples cannot be obtained, study drug administration may be continued provided that the following criteria are met:

The study drug may be dispensed if:

1. There is at least 1 post-Baseline lab assessment (either Week 2 or Week 4 visit)
AND
2. The investigator has reviewed all prior laboratory results and confirms and discusses with the subject via a phone/video call that there is no safety concern for the subject to continue use of the study drug in the absence of current labs
AND
3. No longer than 4 weeks have passed from the last safety lab tests.

Study drug may be shipped from the study site directly to the study subject's home if all the following criteria are met:

- Direct-to-patient (DTP) shipment of study drug is allowed by local regulations and the relevant ethics committee
- Subject agrees to have the study drug shipped directly to their home
 - Shipments may also include other study supplies (e.g., drug dosing diaries, paper copies of PROs). Instructions will be provided by AbbVie as to how a study site can initiate a DTP shipment using Marken, a global vendor selected by AbbVie to provide this service when necessary. Shipments of study drugs from the study site to a subject's home will be appropriately temperature controlled (qualified shipper or temperature monitoring) within the labeled storage conditions. Signature is required upon delivery;

due to COVID-19 related social distancing, this may be provided by the courier after delivery. Documentation of the shipment is to be retained by the clinical site.

- AbbVie will not receive subject identifying information related to these shipments, as the site will work directly with the courier.

The study site is responsible for meeting IRB/IEC reporting requirements related to DTP shipments of study drug, and for obtaining consent to provide delivery information to the courier and documenting this consent in source documents.

DTP study drug shipment will be allowed on the study for the duration of the COVID-19 pandemic and will be removed once the pandemic is considered to be resolved.

Mayo Score/Partial Mayo Score

Data from the subject diaries will be collected in order to calculate Mayo Score/Partial Mayo Score at the time points indicated in [Appendix C](#) and [Appendix D](#).

Whenever possible, the same physician (investigator or sub-investigator) should determine the Physician's Global Assessment (PGA) subscore for an individual subject through the duration for the study. The directions for capturing the stool frequency subscore (SFS), rectal bleeding subscore (RBS), and PGA subscores of the Mayo score are described in [Appendix F](#).

Diary entries from the most recent 3 consecutive days prior to the visit should be utilized for calculation purposes. If diary entries from the 3 most recent consecutive days prior to the visit are not available, the 3 most recent consecutive days in the last 10 days will be utilized. If data are not available for 3 consecutive days, the average of the entries from the most recent 3 non-consecutive days in the last 10 days will be utilized.

Endoscopy

All endoscopies should be recorded in a color video format at the time points noted in [Appendix C](#) and [Appendix D](#). There will be a window of 7 days prior to the scheduled

visit to conduct the endoscopy. For the screening endoscopy, this procedure may be completed at any time during the Screening Period but not on the date the subject is randomized as the central reader review of the endoscopy video is required for study entry (central reading can take up to 3 business days). For other scheduled visits, the endoscopy may not occur after the visit, only on the day of or in advance of the scheduled visit. This window may be extended as necessary after consultation with the AbbVie TA MD in case of external, not subject-related circumstances (e.g., scheduling conflict).

Endoscopies will be reviewed by a primary central reader who is blinded to the subject's clinical data, the site's endoscopy assessment and the subject's therapy. If, in the assessment of the endoscopist at the site, the Screening endoscopy shows a normal colonic mucosa, the subject should be screen-failed and the video should not be sent for central reading. The endoscopy will be used for calculation of the endoscopy subscore of the Mayo Score. The endoscopy subscore will be documented by the endoscopist at the site and maintained in the subject's source documents. In addition to endoscopic evaluation using Mayo endoscopic sub-score, the endoscopy findings using the Ulcerative Colitis Endoscopic Index of Severity (UCEIS) scoring system will be used for additional exploratory analyses. During all endoscopy procedures, the endoscopist at the site should determine the segment where there is a clear demarcation between normal and inflamed mucosa and document the distance from the anal verge (in centimeters) in the eCRF.

Screening Endoscopy: A full colonoscopy will be performed at Screening. The endoscopy subscore result from the central reader will be entered into the eCRF by the site and used to evaluate the eligibility of a subject at Baseline for the study. The central reader's assessment will be used in the Mayo score calculations for all efficacy endpoint assessments.

Week 8 (Part 1), Week 16 (Part 2 – Extended Treatment Period) Endoscopy: The Week 8 endoscopy may be either a full colonoscopy or a flexible sigmoidoscopy depending on the extent of the disease at Screening. The endoscopy should be performed up to the segment where a clear demarcation of inflammation is observed. For subjects that entered Part 2 (Extended Treatment Period), an endoscopy will be performed at

Week 16. A flexible sigmoidoscopy is recommended at Week 16; however, the use of a flexible sigmoidoscopy or colonoscopy will be based on the investigator's discretion per local practice. The site's endoscopist scoring will be entered into the eCRF by the site and used for the Mayo score calculation for the purposes of re-randomization into Substudy 3. For the Week 8 or Week 16 re-randomization, the local reading will be compared with the baseline central reading in order to determine clinical response status. The central reader's assessment will be used for the Mayo scores used in all efficacy endpoint assessments.

The same endoscopist should, where possible, perform all endoscopies for an individual subject throughout the study. In addition, where possible, the investigator or subinvestigator should be the endoscopist for the study. The endoscopy subscores by segment will be noted in the subject's source documents and in the database but the central reader's endoscopy subscore will be used for the efficacy analyses.

COVID-19 Pandemic-Related Acceptable Protocol Modifications

If an Endoscopy required at Week 8 and Week 16 is not able to be scheduled at the study site in the required protocol window due to COVID-19, then this may be performed ± 7 days from the planned visit and can be completed at a different Hospital/facility.

If the endoscopy cannot be performed during this extended window at the site or another location, please refer to the guidance for subjects outlined in Section 5.1.

Biopsy During Endoscopy

Appropriate documentation of biopsy results consistent with the diagnosis of UC, in the assessment of the investigator, must be available in order to confirm the subject's eligibility for the study. If this documentation is not available a diagnostic biopsy from the most affected observed area of the colon must be performed during the Screening endoscopy and read by a qualified local pathologist and the results reviewed by the investigator, the central laboratory will not provide a pathology report during the screening endoscopy to document UC diagnosis. Biopsies to rule out dysplasia and colon

cancer may be taken per the investigator's discretion during any endoscopy performed during this study and evaluated by the local pathologist.

Biopsies sent to the central laboratory will not be returned to sites and will be retained for study use only.

Obtainment of biopsy samples should also be recorded on the video.

The signed pathology report will be monitored by the responsible clinical research associate and kept with the subject's source documents onsite. Subjects should not be enrolled if high grade colonic dysplasia or colon cancer is discovered at the Screening endoscopy. Subjects may be enrolled if low grade colonic dysplasia is discovered during endoscopy and is completely removed. If a diagnosis of high grade colonic dysplasia or colon cancer is discovered during any subsequent endoscopic evaluation during the course of the study, the findings should be recorded as an AE and the subject should be discontinued from the study. If low grade colonic dysplasia is discovered during any subsequent endoscopic evaluation during the course of the study, the findings should be entered as an AE and the subject can continue in the study if the lesion has been completely removed.

During all endoscopies up to 3 sets of biopsies are to be collected; one mandatory set of biopsies and, if consented for, two optional sets of biopsies. Each set of biopsies should consist of 2 samples each obtained from the rectosigmoid colon (approximately 15 – 30 cm from the anal verge) for histologic assessment. For each set of 2 samples, one should be taken from the area of most inflammation (if the area is ulcerated, the sample should be obtained from the edge of the ulcer), and one from an area that is representative of the general degree of mucosal inflammation present in that segment. For all histology biopsies, the location of the biopsy specimen (distance from the anal margin) should be recorded.

For China only: only a single biopsy at each endoscopy from the most inflamed area (HistoMOST) will be required per local requirements. The single, required biopsy will be

taken from the area of most inflammation (if the area is ulcerated, the sample should be obtained from the edge of the ulcer) for histologic assessment at each required timepoint as per [Appendix C](#).

For follow-up endoscopies, in the absence of any visible lesions or areas of general inflammation characteristic of UC, up to 3 sets of biopsies should be collected from normal mucosa in the same segments as noted above.

Biopsy Sample Collection, Storage and Shipping:

Biopsies performed to confirm the diagnosis of UC or to rule out current dysplasia/malignancy should be processed and read locally per site standards.

Biopsy specimens per subject should be obtained by endoscopy for histologic assessment at the time points indicated in [Appendix C](#) and [Appendix D](#). Using routine forceps for tissue collection, obtain the required number of biopsy specimens and process the specimens following the instructions in the study-specific laboratory manual.

Intestinal Tissue Analysis

The following analyses will be sent to the central laboratory and performed on tissue samples:

- Qualitative UC histological assessment using Geboes histologic activity score,²⁵ and other histologic scoring systems. These samples may not be read in real time, however if unexpected findings, such as dysplasia, are noted on the histology biopsies, the central laboratory will contact the investigator to inform him/her about the unexpected finding. Subjects who are found to have high grade colonic dysplasia on the submitted biopsy will be terminated from the trial at the time the dysplasia is discovered. Unexpected findings should be recorded as an adverse event.
- Subjects will have the option to provide tissue biopsies (per local requirements) for future exploratory research and/or validation studies. For more information, please refer to Section [5.3.1.2](#).

COVID-19 Pandemic-Related Acceptable Protocol Modifications

Biopsy completion should follow the endoscopy guidance if the visit is affected by COVID-19. If an endoscopy is completed at an alternative location from the study site the study required biopsy is not required. Biopsy can be completed per endoscopist's discretion for local evaluation.

Follow-Up Period

Subjects will be contacted approximately 30 days after the last administration of study drug to obtain information on any new or ongoing adverse events (AEs). If subject is enrolled into Substudy 3 of Study M14-234 they would not be required to complete the follow-up period in Study M14-675 and would be completed under that protocol, as applicable.

During this follow-up call the results of the follow-up at home pregnancy test should be communicated to the site and follow reporting found in Section 6.1.6.

Subjects may discontinue study drug treatment at any time during study participation. Subjects that end study participation early will have a Premature Discontinuation (PD) Visit and complete the procedures outlined for the PD Visit in [Appendix C](#) and [Appendix D](#) as soon as possible after the last dose of study drug and preferably prior to the administration of any new therapies.

Unscheduled Visits

An Unscheduled Visit should be performed when the subject comes in for a medical visit for evaluation and assessment. During Unscheduled Visits, blood and urine samples will be obtained for the laboratory tests listed in [Table 1](#), or for other tests at the investigator's discretion.

Visits for dispensing new study drug in case of temperature excursion, loss or damage are not considered an Unscheduled Visit. In addition, visits to only retest a lab will not be considered an Unscheduled Visit.

Home Healthcare Service Due to COVID-19 Pandemic

Subjects may be offered the option of home healthcare visits provided by a licensed health care provider, such as a study nurse or third-party vendor. Study procedures conducted in the home setting may include physical examination, vital signs, laboratory tests and Patient Reported Outcomes. This option can only be offered in countries and sites that comply with local regulatory and IRB/IEC requirements for homecare.

Finally, it is recommended that medical personnel entering a subject's home adhere to local health regulations during the COVID-19 pandemic, such as the use of Personal Protective Equipment (PPE), as required.

Protocol deviations must be recorded per AbbVie's standard process.

If the home visits will not be performed by site personnel, the site may be responsible for selecting a vendor, contracting with a vendor, and for ensuring continued compliance with the terms of the Clinical Study Agreement.

Individuals performing home visits need to be added to the delegation log.

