3.2 Benefits and Risks

Despite the availability of various UC therapies, including biologic therapies such as anti-TNFs, many patients still do not respond adequately to these treatments, or gradually lose response over time. Thus, there remains a clear medical need for additional therapeutic options in UC for patients with inadequate response to, loss of response to, or intolerance to conventional therapies but have not failed biologic therapy.

Clinical efficacy of JAK inhibition has been demonstrated in the treatment of UC. Tofacitinib is recently approved for the treatment of UC.²¹ However, the non-selectivity of tofacitinib targeting JAK1, JAK2 and JAK3 has been associated with a number of safety issues.^{17-19,22,23}

Upadacitinib is a novel JAK1 selective inhibitor with minimal inhibitory effects on JAK2 and JAK3, which could potentially minimize some of the reported safety concerns with non-selective JAK inhibition which are thought to be mediated by inhibition of JAK2 and JAK3 signaling pathways.

The available long-term safety data from the Phase 3 rheumatoid arthritis (RA) studies with upadacitinib did not show any new significant safety concerns compared to the marketed JAK inhibitors. The findings of an increased risk of infections, herpes zoster, and abnormal laboratory changes have been observed (e.g., elevations of serum transaminases, lipids, creatine phosphokinase, and reductions in hemoglobin and white blood cells) with upadacitinib. The incidence rates of other clinically important adverse events such as cardiovascular events, malignancies and mortality reported during the RA studies were within the expected range for the general population or for a population of patients with moderately to severely active RA. Events of deep vein thrombosis (DVT)

and pulmonary embolism (PE) have been reported in patients receiving JAK inhibitors including upadacitinib.

The results of genetic toxicology testing indicate that upadacitinib is not genotoxic; however, upadacitinib is teratogenic based on animal studies, which necessitates avoidance of pregnancy in females of childbearing potential. Based on the calculated safety margins for human fetal exposure with seminal fluid transfer, there is judged to be no risk to the pregnancy of female partners of male subjects who are treated with upadacitinib. Male trial participants are therefore not required to use contraception when participating in upadacitinib clinical trials.

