5.2.4 Contraception Recommendations

Contraception Recommendation for Females

Subjects must follow the following contraceptive guidelines as specified.

Females of Non-childbearing Potential:

Females do not need to use birth control during or following study drug treatment if considered of non-childbearing potential due to meeting any of the following criteria:

- Postmenopausal, age > 55 years with no menses for 12 or more months without an alternative medical cause.
- Postmenopausal, age ≤ 55 years with no menses for 12 or more months without an alternative medical cause AND a follicle-stimulating hormone (FSH) level > 40 IU/L.
- Permanently surgically sterile (bilateral oophorectomy, bilateral salpingectomy, or hysterectomy)

Females of Childbearing Potential:

Females of childbearing potential must avoid pregnancy while taking study drug(s) and for at least 30 days after the last dose of study drug. Females must commit to one of the following methods of highly effective birth control:

- Combined (estrogen and progestogen containing) hormonal contraception (oral, intravaginal, transdermal, injectable) associated with the inhibition of ovulation, initiated at least 30 days prior to Study Baseline.
- Progestogen-only hormonal contraception (oral, injectable, implantable) associated with inhibition of ovulation, initiated at least 30 days prior to Study Baseline.
- Bilateral tubal occlusion/ligation (can be via hysteroscopy, provided a hysterosalpingogram confirms success of the procedure) (For Japan: only bilateral tubal ligation).
- Vasectomized partner(s) provided the vasectomized partner has received medical confirmation of the surgical success and is the sole sexual partner of the trial participant.
- Intrauterine device (IUD).
- Intrauterine hormone-releasing system (IUS).
- True abstinence (if acceptable per local requirements): defined as refraining from heterosexual intercourse when this is in line with the preferred and usual lifestyle of the subject (periodic abstinence [e.g., calendar, ovulation, symptothermal, post-ovulation methods] and withdrawal are not acceptable).

- In the US, true abstinence applies only to women of childbearing potential who do not have male partners and are not engaging in heterosexual intercourse as their preferred and usual lifestyle (periodic abstinence [e.g., calendar, ovulation, symptothermal, post-ovulation methods] and withdrawal are not acceptable).

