- For subjects in Ireland and Argentina, a repeat serum pregnancy test ≥ 3 days later that is still borderline will result in screen failure. (A borderline serum pregnancy test may be repeated more than once during the screening period.)

Women of childbearing potential includes all women who are not surgically sterile (both ovaries and or both fallopian tubes removed or uterus removed) or post-menopausal (defined as at least 55 years of age with no menses for at least one year, without an alternate medical reason for amenorrhea, or less than 55 years of age with no menses for

at least one year, without an alternate medical reason for amenorrhea and a FSH level > 40 IU/L).

Women of childbearing potential will have a urine pregnancy test performed locally by designated study personnel at Baseline and all subsequent visits.

Women of childbearing potential will also have a urine pregnancy test performed at home 30 days after the last visit. The results of follow up pregnancy test should be communicated during the telephone follow up call.

If any urine pregnancy test is positive, a serum pregnancy test will be performed by the central laboratory. If the serum pregnancy test is positive, dosing must be stopped and the subject must be discontinued from the study or, if pregnancy identified at end of study visit, pregnancy must be reported to AbbVie as outlined in Section 6.1.6.

A lactating or pregnant female will not be eligible for participation or continuation in this study.

If during the course of the study a woman becomes surgically sterile or postmenopausal and complete documentation as described in Section 5.2.4 is available, pregnancy testing is no longer required.

COVID-19 Pandemic-Related Acceptable Protocol Modifications

Monthly urine pregnancy testing must be performed for women of child-bearing potential and results confirmed prior to administration of study drug to the subject. Urine pregnancy tests may be performed at the local lab or at home and confirmed by site staff via phone, telemedicine or video call. Pregnancy test results must be available before drug dispensation.

Hepatitis Screen

All subjects will be tested for the presence of HBV and HCV at Screening.

Hepatitis B

[figure not shown]
Subjects will be tested for the presence of HBV at screening using the following tests:

- HBs Ag (Hepatitis B surface antigen)
- HBc Ab/anti-HBc (Hepatitis B core antibody)
- HBs Ab/anti-HBs (Hepatitis B surface antibody)

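### Protocol 5.2.4 and 5.3.1.1 define post-menopausal differently at age 55, so the same woman can need contraception under one section and fall outside the pregnancy-testing group of the other

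*Protocol*

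**What the plan says.** Protocol 5.2.4 (Contraception Recommendations) exempts a woman from birth control without an FSH result only if she is "Postmenopausal, age > 55 years with no menses for 12 or more months without an alternative medical cause". At 55 or younger it adds a laboratory condition: "Postmenopausal, age ≤ 55 years with no menses for 12 or more months without an alternative medical cause AND a follicle-stimulating hormone (FSH) level" above 40 IU/L. A woman who meets neither rule and is not surgically sterile is of childbearing potential, and then "Females must commit to one of the following methods of highly effective birth control".

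Protocol 5.3.1.1 (Pregnancy Tests) carries its own definition. It accepts as "post-menopausal (defined as at least 55 years of age with no menses for at least one year" a woman with no FSH result, provided that there is no other medical reason for the amenorrhoea. The same FSH threshold applies only to the next group, "or less than 55 years of age with no menses for" at least a year. The consequence is stated in the same section: "Women of childbearing potential will have a urine pregnancy test performed locally by designated study personnel at Baseline and all subsequent visits". That section also ties the Screening serum test, the home test 30 days after the last visit and the pandemic-period rule on having a result before dispensing to childbearing potential.

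The reason for these precautions is in Protocol 3.2: "upadacitinib is teratogenic based on animal studies, which necessitates avoidance of pregnancy in females of childbearing potential".

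**The concern.** The two definitions use the same elements (age, a year of amenorrhoea, no other cause, FSH above 40 IU/L) but put age 55 on opposite sides of the line. A site that follows 5.2.4 asks a 55-year-old for an FSH result or contraception. A site that follows 5.3.1.1 has no reason to obtain an FSH result and may leave her out of pregnancy testing.

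Whether a safety check is applied should not depend on which section is open. There is also a compliance side. Under the 5.2.4 definition her missing tests are departures from the protocol; under 5.3.1.1 they are not. A missing Screening or Baseline test could even be read as entry without meeting the criteria, which Protocol 7.0 makes reportable and SAP Appendix A counts.

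**Working it through.** No figure in the plan is at issue, so the check sets the two rules side by side.

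**Test case.** A woman with no menses for at least 12 months, no other medical cause, not surgically sterile, and no FSH result above 40 IU/L (not measured, or measured at 40 or below). Age is counted in completed years. Age 55 is inside the eligible range of 16 to 75 (Protocol 5.2.1, criterion 1).

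| Age | 5.2.4: FSH needed if age is 55 or less | 5.3.1.1: FSH needed if age is under 55 | Agree? |
|---|---|---|---|
| 54 | childbearing potential | childbearing potential | yes |
| 55 | childbearing potential | post-menopausal | no |
| 56 | post-menopausal | post-menopausal | yes |

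**Conditions that remove the conflict.** If she still menstruates, both rules class her as of childbearing potential. If she is surgically sterile, or has FSH above 40 IU/L with a year of amenorrhoea, both exempt her.

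**How age is counted.** If age is taken exactly, a woman of 55 years and 6 months is both over 55 and at least 55, so the rules agree. The gap then shrinks to the 55th birthday itself. Neither section says which reading applies.

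**Do the cross-references settle it?**
- Synopsis inclusion criterion 5 ties the Screening and Baseline tests to 5.2.4. The full criterion 5 in Protocol 5.2.1 has no such reference.
- In 5.3.1.1, a woman who becomes post-menopausal during the study stops testing only with the documentation described in 5.2.4.
- The last line of 5.2.4 sends the reader to 5.3.1.1 for pregnancy testing.

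Two references point to 5.2.4 and one points back, so the protocol also conflicts with itself on whether she is tested.

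**Is a missing FSH result plausible?** FSH does not appear in the laboratory list (Protocol Table 1) or the activity schedule (Appendix C), as far as these tables can be read.

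**Size.** The documents give neither the share of women nor their age distribution. Assume that 40-45% of the 462 subjects are women and that 1.5-2% of those are aged 55:

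- low: 462 × 0.40 × 0.015 = 2.8
- high: 462 × 0.45 × 0.02 = 4.2

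That is about 3 to 4 women aged 55, before removing those who menstruate, are sterile or have FSH above 40 IU/L.

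**The case against.** The strongest reply is that this is a boundary slip (over 55 against at least 55) with almost no reach. Several parts of that reply stand.

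- **Contraception still applies.** Avoiding pregnancy is what Protocol 3.2 demands, and the means is contraception, required through inclusion criterion 6 and 5.2.4. This woman stays under that requirement. Only the check by testing is in doubt.
- **Testing is not plainly lost.** A reader might infer that her tests simply lapse. The documents do not support that: synopsis criterion 5 ties the Screening and Baseline tests to 5.2.4, and the change-of-status rule does the same. But these references do not amend the definition in 5.3.1.1, and 5.2.4 itself hands testing to that section.
- **Not every woman of 55 is affected.** A reader might take the conflict to cover any 55-year-old without an FSH result. It needs the amenorrhoea, the absence of another cause, no surgical sterility, and age in completed years.
- **The hazard is stated from animal data.** The rationale tables for the inclusion and exclusion criteria call the effect on pregnancy unknown.
- **It is late.** The synopsis is dated 31 July 2020 with screening closed. SAP Appendix D puts the last randomisation at 26 May 2020. Week 8 for that subject is 56 days later, 21 July (28 July with the 7-day pandemic window), and Week 16 is 112 days later, 15 September. After the amendment, only Part 2 visits and follow-up remained.

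These points limit the size and urgency. None of them makes the two definitions agree.

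**Conclusion.** The conflict is real and minor. It is an internal inconsistency, not a design choice. It concerns only women recorded as 55 who meet every condition of the test case: a handful at most, possibly none. The count rests on assumed shares of women and of 55-year-olds, and the gap itself rests on age in completed years.

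A reader might conclude that women were exposed to a teratogenic drug without protection. The documents do not support that, because 5.2.4 keeps this woman under contraception and parts of the protocol point towards testing her. What they do support is that two operative rules give different answers for the same woman, with no statement of which governs. Efficacy, sample size, power and alpha are unaffected.

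**What to change.** Reconcile Protocol 5.2.4 and 5.3.1.1 to one definition of post-menopausal, and state how age is counted. Use that definition for contraception, for every pregnancy test (Screening, visits, 30-day home test, pandemic-period dispensing rule) and for women whose status changes during the study. Make the synopsis and full versions of inclusion criterion 5 refer to the same place. This review does not say which cut-off should be adopted.

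Notify sites. Because enrolment is over, also check the records of women entered at age 55: how each was classified, whether an FSH result exists, and which tests were done.

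The cost is a one-line clarification, a site notice and a review of very few records. No analysis changes.
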